14.3.7.2 Efficacy over time

To further explore possible early onset of effect and general efficacy over time, the following endpoints will be evaluated at each scheduled assessment up to Week 14 or each week up to Week 15:

- IGA TS at each scheduled assessment until Week 14.
- PaGA TS at each scheduled assessment until Week 14.
- Change from baseline to each week through Week 1 to 15 in HESD NRS (weekly average for each individual symptom).
 - Reduction of worst pruritus (weekly average) – one of the symptoms captured in the HESD – of at least 4 from baseline to each week through Week 1 to 15 among subjects with baseline worst pruritus (weekly average) of at least 4.
- Change from baseline to each scheduled assessment until Week 14 in HEIS (for each individual item).
- Change in DLQI score from baseline to each scheduled assessment until Week 14.
- Reduction of DLQI of at least 4 from baseline to each scheduled assessment until Week 14.

For the binary endpoints, the same Cochran-Mantel-Haenszel test as for the Week 16 assessment will be applied. For the continuous endpoints, the repeated measurements model already described previously for the Week 16 assessments facilitates that the p-values, treatment differences and 95% CIs can be derived for each visit up to Week 14 (or Week 15 for the change in HESD NRS (weekly average)).

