
To evaluate the effect of delgocitinib on Staphylococcus aureus colonisation of the skin, skin microbiome, skin barrier function, and skin inflammation.
	
 Reduction in Dermatology Life Quality Index (DLQI) of ≥ 4 points from baseline to Week 16 among subjects with baseline DLQI ≥ 4. Change in DLQI score from baseline to Week 16. Change in EuroQoL 5-dimension 5-level questionnaire (EQ-5D-5L) from baseline to Week 16. Change in Quality of Life in Hand Eczema Questionnaire (QOLHEQ) from baseline to Week 16. Change in Work Limitation Questionnaire (WLQ) from baseline to Week 16. 
Efficacy over time
 
 IGA TS at each scheduled assessment until and including Week 14. PaGA TS at each scheduled assessment until and including Week 14. Change from baseline to each week from Week 1 to Week 15 in HESD (weekly average for each individual symptom). 
 Reduction of worst pruritus (weekly average) of ≥ 4 points from baseline to each week from Week 1 to Week 15 among subjects with baseline worst pruritus (weekly average) ≥ 4. Change from baseline to each scheduled assessment until Week 14 in HEIS. Change in DLQI score from baseline to each scheduled assessment until Week 14. Reduction of DLQI of at least 4 points from baseline to each scheduled assessment until Week 14. 
Biomarkers
 
 Change in Staphylococcus aureus colonisation from baseline to Week 16. Change in microbiome composition from baseline to Week 16. Change in skin barrier function, measured as transepidermal water loss, capacitance, skin pH, and content of natural moisturising factors, from baseline to Week 16. Change in expression of skin barrier proteins and in extent of immune cells in skin biopsies from baseline to Week 16.

7 Trial design

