8.2 Inclusion criteria

For inclusion into this trial, subjects must fulfil all of the following criteria:

1. Signed and dated informed consent has been obtained prior to any protocol-related procedures.
2. Age 18 years or above.
3. Diagnosis of chronic hand eczema defined as hand eczema, which has persisted for more than 3 months or returned twice or more within the last 12 months.
4. Disease severity graded as mild to severe according to Investigator's Global Assessment (i.e., an IGA score of 2 or more).
5. Recent history (within 1 year before the screening visit) of inadequate response to topical corticosteroid treatment or topical corticosteroid treatment being medically inadvisable.
6. Diagnostic patch testing performed within 3 years prior to the screening visit.
7. A woman of childbearing potential* must use a highly effective** form of birth control throughout the trial and for at least 2 weeks after last application of IMP.

* A woman is defined as not being of childbearing potential if she is postmenopausal (at least 12 months with no menses without an alternative medical cause prior to screening), or surgically sterile (hysterectomy, bilateral salpingectomy, or bilateral oophorectomy).

**A highly effective method of birth control is defined as one which results in a low failure rate (less than 1% per year) such as bilateral tubal occlusion, intrauterine device, intrauterine hormone-releasing system, combined (estrogen and progestogen containing) hormonal contraception associated with inhibition of ovulation (oral, intravaginal, transdermal), progestogen-only hormonal contraception associated with inhibition of ovulation (oral, injectable, implantable), sexual abstinence (when this is in line with the preferred and usual life style of the subject), vasectomised partner (given that the subject is monogamous).

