In the subgroup of subjects with a baseline DLQI score of at least 4, the proportion of subjects with a reduction in DLQI score of at least 4 at Week 16 will be summarised by treatment group and analysed using the Cochran-Mantel-Haenszel approach as described for the analysis of the primary endpoint.

The change from baseline to Week 16 in HESD NRS (weekly average for each individual symptom), HEIS (for each individual item), DLQI, EQ-5D-5L, QOLHEQ, and WLQ will be summarised by treatment group and domain, where applicable, and analysed using the MMRM approach as described above for the analysis of the secondary continuous endpoint.

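### The DLQI 4-point responder endpoint is limited to baseline DLQI of 4 or more at Week 16 but not at the earlier visits, so the early rates and the Week 16 rate have different denominators

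*Combined protocol and SAP*

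**What the plan says.** **Week 16.** Section 14.3.7.1 sets the 4-point threshold for a DLQI response and analyses it with a restriction, "In the subgroup of subjects with a baseline DLQI score of at least 4". Panel 3 (Section 6) agrees, defining the reduction as "points from baseline to Week 16 among subjects with baseline DLQI" of at least 4.

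**Earlier visits.** Section 14.3.7.2 lists "Reduction of DLQI of at least 4 from baseline to each scheduled assessment until Week 14". Panel 3 lists "Reduction of DLQI of at least 4 points from baseline to each scheduled assessment until Week 14". Neither limits the endpoint by baseline DLQI.

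**The parallel pruritus endpoint.** In the same list in Section 14.3.7.2, the 4-point pruritus reduction is assessed "from baseline to each week through Week 1 to 15 among subjects with baseline worst pruritus (weekly average) of at least 4". Panel 3 also keeps that restriction for the earlier weeks.

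**Method for the earlier visits.** Section 14.3.7.2 states: "For the binary endpoints, the same Cochran-Mantel-Haenszel test as for the Week 16 assessment will be applied".

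**Who can be in the denominator.** The severity criterion in Section 8.2 is "Disease severity graded as mild to severe according to Investigator's Global Assessment", that is, IGA of 2 or more. None of the inclusion criteria sets a minimum DLQI. Under Section 14.2 the full analysis set is all randomised subjects.

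**The concern.** A responder rate can be followed over time only if the same subjects can respond at every time point. The Week 16 restriction exists because a subject who starts below 4 has no room to fall by 4. Without it, the early analyses count such subjects as non-responders whatever the treatment does. Early rates and early differences from vehicle would be pulled down, and the denominator would change between Week 12 and Week 16. Part of any rise at Week 16 could then come from that change and not from treatment. Section 14.3.7.2 is there to explore early onset and efficacy over time, and the mismatch blurs that comparison for this endpoint.

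**Working it through.** **Plan's own figure.** The plan gives no expected rate, power or baseline distribution for the DLQI responder endpoint. Its only power statement (Section 14.1) concerns IGA treatment success and does not bear on this point.

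**Inputs from the documents**
- DLQI has 10 items scored 0 to 3 (Section 11.7.1.5), so the total runs from 0 to 30. A baseline of 0, 1, 2 or 3 allows a fall of at most 3.
- DLQI is scheduled after baseline at Weeks 1, 4, 8, 12 and 16 (Panel 2). The visits affected are Weeks 1, 4, 8 and 12; there is no DLQI at Week 14.
- 50 subjects per arm; two-sided 5% level (Sections 14.1 and 14.3.12).

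**Assumptions (not in the documents)**
- p, the share with baseline DLQI below 4, taken as 0% to 30% and equal across arms.
- Response among subjects with baseline DLQI of 4 or more: 60% on active and 40% on vehicle, constant over time.

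**Formulas.** Let r be the response rate among subjects who can respond. Those who cannot respond contribute zero, so:
- rate among all randomised = (1 − p) × r + p × 0 = (1 − p) × r
- difference from vehicle = (1 − p) × (r_active − r_vehicle)
- step at Week 16 caused by the denominator alone = r − (1 − p) × r = p × r

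For p = 20%: 0.8 × 60 = 48; 0.8 × 40 = 32; difference 16 points; step on active 0.2 × 60 = 12 points.

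| p (assumed) | Early rates, active/vehicle | Early difference (points) | Week 16 rates | Step on active (points) |
|---|---|---|---|---|
| 0% | 60/40 | 20 | 60/40 | 0 |
| 5% | 57/38 | 19 | 60/40 | 3 |
| 10% | 54/36 | 18 | 60/40 | 6 |
| 20% | 48/32 | 16 | 60/40 | 12 |
| 30% | 42/28 | 14 | 60/40 | 18 |

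The ratio of the two rates does not change, because (1 − p) cancels. If p differs between strata, a stratified difference will shrink by approximately, not exactly, this factor.

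**Does keeping everyone in gain power?** Unstratified pairwise power, normal approximation with pooled variance under the null: power = Φ{[√n × |d| − 1.96 × √(2 × m × (1 − m))] / √(a(1 − a) + v(1 − v))}, where a and v are the two rates, d = a − v and m is their mean.

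| p | All randomised, n = 50 per arm | Baseline DLQI ≥4 only, n = 50 × (1 − p) per arm |
|---|---|---|
| 0% | 51.6% | 51.6% |
| 5% | 47.7% | 49.6% |
| 10% | 43.9% | 47.5% |
| 20% | 37.0% | 43.1% |
| 30% | 30.9% | 38.5% |

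In this example the unrestricted analysis has slightly lower power despite its larger denominator. With the same restriction at every visit, the step is zero for any p.

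**The case against.** **The wording may be shorthand.** The sentence "For the binary endpoints, the same Cochran-Mantel-Haenszel test as for the Week 16 assessment will be applied" can be read as carrying the whole Week 16 analysis back to the earlier visits, subgroup included, and nothing says outright that the early analysis uses all randomised subjects. But the sentence names a test, not a population, and the pruritus item in the same list repeats its own restriction. Someone programming from this text would reasonably treat the two endpoints differently. If the restriction was intended, the text still needs to say so.

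**The comparison between arms remains valid.** This stands. Subjects who cannot respond are spread over the arms by randomisation and count as non-responders in each. A rate among all randomised subjects is a legitimate quantity and favours no arm. The fault is that it is a different quantity from the one at Week 16.

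**The size is assumed.** This also stands. The documents give neither a baseline DLQI distribution nor DLQI response rates.

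**The time course is covered elsewhere.** IGA treatment success by visit, HECSI by visit and change in DLQI by visit are all planned, and the DLQI change analysis has no baseline cut-off at any visit. This limits the consequence but does not remove the inconsistency.

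**The statistical analysis plan may settle it.** Section 14.3.12 has the analyses reviewed on blinded data and that plan finalised before the code is broken. Its separate text cannot be seen here, so whether it states the denominator cannot be checked.

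**Conclusion.** Wrong as written: an internal inconsistency that costs nothing to correct. Run as stated, the DLQI responder analyses at Weeks 1, 4, 8 and 12 use a wider denominator than Week 16. Early rates and crude differences are scaled by about (1 − p), assuming p is similar across arms. The size is unknown and could be near zero; it is exactly zero if every subject has a baseline DLQI of at least 4. Type I error and the primary and secondary endpoints are unaffected. The endpoint is exploratory and listed under the other endpoints, so priority is low.

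A reader might infer more than the documents support:
- **That a marked artificial jump at Week 16 is certain.** It depends on p, which is not given.
- **That p can be read from the 20% to 30% of subjects planned to have mild disease.** That range is for IGA; no section links mild IGA to a DLQI below 4.
- **That entry depends on IGA alone.** Section 8.2 also requires chronic disease, inadequate response to topical corticosteroids or their being inadvisable, and patch testing. What is supported is only that no minimum DLQI applies.
- **That the choice of phase 3 treatment duration would be misled.** Section 5.3 refers to the results of the whole trial, and nothing ties that decision to this endpoint.

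**What to change.** In Panel 3 and in Section 14.3.7.2, limit the by-visit DLQI responder endpoint to subjects with a baseline DLQI of at least 4, matching the Week 16 definition ("In the subgroup of subjects with a baseline DLQI score of at least 4") and the pruritus endpoint. Report the number of subjects in the denominator by arm at each visit. If a rate among all randomised subjects is also wanted, give it as a labelled supplement at every visit, Week 16 included.

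Make the change before unblinding, so that the denominator is not chosen after results are seen. Section 14.3.12 allows changes to the planned analysis to be described in an amendment or in the statistical analysis plan. The cost is one phrase in two places; no new data, visits or subjects are needed.

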14.3.7.3 Exploratory analyses

Treatment effect within each subtype of chronic hand eczema in terms of disease aetiology will be explored for the primary and secondary endpoints using the same analysis methods as described previously.

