5.1 Chronic hand eczema

Chronic hand eczema is an inflammatory skin disorder located anywhere on the hands and wrists. It is clinically characterised by erythema, infiltration, hyperkeratosis, oedema, and vesicles. Secondary signs include scaling, fissures, and erosions, and the condition may be exacerbated by bacterial infections. Important symptoms include itching and pain, and the disease is often characterised by chronic relapses and a poor prognosis. According to the guideline developed by the European Society of Contact Dermatitis (1), chronic hand eczema refers to hand eczema, which persists for more than 3 months or relapses twice or more often per year.

Hand eczema is usually multifactorial and there is no reliable connection between morphology and aetiology of the disease. Based on aetiology, eczema is commonly divided into exogenous or endogenous types. The most common aetiologies of hand eczema are found to be the exogenous types irritant contact dermatitis (35%) and allergic contact dermatitis (19%), and the endogenous type atopic hand dermatitis (22%) (2).

The severity of hand eczema varies from mild to severe and may cause significant pain and discomfort in daily life. General embarrassment is also associated with the disease due to its visible location (3). Hand eczema can result in impaired quality of life and decreased working capacity, imposing a great economic burden on patients and society. In Denmark, an 8-year follow-up study in a cohort of 274 people with hand eczema found that 12.4% had been on sick leave and 8.5% had changed jobs because of their hand eczema (4). Similarly, prolonged sick leave due to occupational hand eczema was reported in approximately 20% of patients in a study from 2005 (5). A US survey found that people with chronic hand eczema report worse quality of life and impaired activity and work performance compared with those without chronic hand eczema (3).

Treatment of chronic hand eczema involves different treatment strategies such as elimination of triggers, general skin care, and anti-inflammatory therapy in a step-wise approach. General skin care in terms of emollients is widely used and recommended by physicians, but evidence of efficacy is sparse (1). Nonetheless, elimination of triggers such as allergens and irritants is effective and a prerequisite for successful therapy on longer term but is in many circumstances difficult to achieve due to the occupational character of the exposure.

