11.2.4 Classification of chronic hand eczema

Based on medical history (including history of diagnostic patch testing within 3 years) and morphology of the present lesions, the investigator will determine the subtype(s) according to the definitions in [Panel 8](#). The subtype(s) of the subject's chronic hand eczema will be recorded as main diagnosis and additional diagnoses, if applicable.

Panel 8: Definition of subtypes of hand eczema

Subtype	Definition
Allergic contact dermatitis	Hand eczema caused by relevant contact allergens or cross-reactors identified by patch testing. Relevance means that there is a current exposure of the allergens to the hands.
Irritant contact dermatitis	Hand eczema with documented irritant exposure, which is quantitatively likely to cause dermatitis. No relevant contact allergy (no current exposure to allergens to which the patient has reacted positive in patch test).
Contact urticaria/protein contact dermatitis	Hand eczema in patients exposed to proteins (food, latex, and other biological material) with a positive prick test, or proven specific IgE, to suspected items. A considerable proportion of patients with contact urticaria will also have atopic symptoms.
Atopic hand eczema	Hand eczema in a patient with a medical history of atopic eczema, previous or current. No documented irritant exposure and/or relevant contact allergen likely to cause eczema.
Pompholyx	Recurrent hand eczema with vesicular eruptions. No relevant contact allergy, no documented irritant exposure likely to cause dermatitis.
Hyperkeratotic eczema (hyperkeratotic dermatitis of the palms)	Chronic eczema with hyperkeratosis in the palms, or pulpitis, and no vesicles or pustules. No documented irritant exposure to the involved skin areas, likely to cause irritant exposure.

Reference: Diepgen et al. 2015 ([1](#)).

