14.1 Sample size

A total of 250 subjects will be divided into 5 treatment groups and randomised 1:1:1:1:1 to one of each dose level of delgocitinib cream (1, 3, 8, or 20 mg/g) or delgocitinib cream vehicle.

The sample size is based on the following pairwise consideration, even though the primary objective of the trial is to establish the dose-response relationship. With a significance level of 5% when comparing 2 treatment groups and assuming treatment success rates (according to IGA) of 45% and 15%, respectively of the investigative treatment group (delgocitinib cream) and delgocitinib cream vehicle, then 50 subjects per treatment group will provide a power slightly above 90% for finding significantly different success rates between treatment groups.

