14.3.12 General principles

Unless otherwise stated, all significance tests will be 2-sided using the 5% significance level. All CIs will be presented with 95% degree of confidence.

An observed-cases approach will be used for tabulations of data by visit (i.e., involving only those subjects who attended each specific visit).

Categorical data will be summarised using the number and percentage of subjects in each category and treatment group. Continuous data will be summarised using the mean, median, standard deviation, minimum, and maximum values.

All the analyses specified in the protocol will be reviewed in relation to the blinded data actually obtained and the statistical analysis plan will be finalised before breaking the randomisation code.

Any changes from the statistical analysis planned in this clinical trial protocol will be described and justified in a protocol amendment, the statistical analysis plan and/or in the CTR dependent on the type of deviation.

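### Section 14.3.7.3 repeats the full-trial analyses inside each aetiological subtype but plans no test or estimate of whether the effect differs between subtypes

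*Combined protocol and SAP*

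**What the plan says.** Section 14.3.7.3 says that the treatment effect in each aetiological subtype will be explored "for the primary and secondary endpoints using the same analysis methods as described previously". The methods this refers back to are:

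- **IGA treatment success (14.3.5):** MCP-Mod with three candidate models, adjusted for region and baseline IGA, and a Cochran-Mantel-Haenszel (CMH) test of each dose against vehicle over 2 regions x 3 IGA levels = 6 strata.
- **Change in HECSI (14.3.6):** the same dose-response modelling, and an MMRM with unstructured covariance over the post-baseline visits.
- **Time to IGA treatment success (14.3.6):** Kaplan-Meier curves and a log-rank test stratified by region and baseline IGA.

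Subtype is assigned under section 11.2.4, where the subtype or subtypes "will be recorded as main diagnosis and additional diagnoses, if applicable". Panel 8 there defines six. No rule says which diagnosis places a subject in a subgroup. Subtype is neither a randomisation stratum (7.2) nor a covariate in any model.

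The only subtype frequencies in the documents are in section 5.1, which names as most common "irritant contact dermatitis (35%) and allergic contact dermatitis (19%), and the endogenous type atopic hand dermatitis (22" per cent). They describe hand eczema in general.

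The trial is sized only for a whole-arm pairwise comparison (14.1).

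**The concern.** The question of interest is whether delgocitinib works differently in different kinds of hand eczema. Section 12 calls the population heterogeneous in aetiology, and section 5.3 says the results will support phase 3. A set of separate within-subtype analyses does not answer that question. A significant result in one subtype and a non-significant one in another is not evidence of a difference, because each result depends heavily on the size of its subgroup.

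There is also a feasibility problem. Methods chosen for about 50 subjects per arm would be applied to fractions of that number. And if additional diagnoses count, subgroups can overlap.

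At stake is a subtype being judged unresponsive, or singled out as responsive, when nothing but chance and subgroup size separates it from the rest.

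**Working it through.** **1. The plan's own figure.** Inputs from 14.1 and 14.3.12: "assuming treatment success rates (according to IGA) of 45% and 15%, respectively"; two-sided 5%; 50 per arm. With difference 0.30 and mean rate 0.30,

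power = Φ{[0.30√n − 1.96√(2 × 0.30 × 0.70)] / √(0.45 × 0.55 + 0.15 × 0.85)}.

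For n = 50: (2.121 − 1.270) / 0.612 = 1.39, so power is 91.8%. This agrees with the statement that "50 subjects per treatment group will provide a power slightly above 90" per cent.

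**2. Subtype sizes (assumption).** Section 5.1 shares applied to 50 per arm: irritant 0.35 × 50 = 17.5; atopic 0.22 × 50 = 11; allergic 0.19 × 50 = 9.5; remainder 0.24 × 50 = 12. Rounded: 18, 11, 10 and 12.

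**3. Power per dose when the true effect is identical (45% against 15%) in every subtype.** The unstratified column uses the formula above. The stratified column is a simulation of the six-stratum CMH test, assuming 80/20 by region (the North American cap is 50 of 250) and 25/50/25 by IGA (within the limits in 7.2). The CI half-width is 1.96√(0.375/n).

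| Subtype | n per arm | Unstratified | Stratified CMH | 95% CI half-width |
|---|---|---|---|---|
| Irritant | 18 | 50% | 45% | 28 points |
| Atopic | 11 | 33% | 27% | 36 points |
| Allergic | 10 | 30% | 24% | 38 points |
| Remainder, pooled | 12 | 35% | 30% | 35 points |
| Full arms | 50 | 92% | – | 17 points |

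**4. Chance of a mixed picture.** If each subject belongs to one subtype, the tests are independent, and P(mixed) = 1 − P(all significant) − P(none significant).

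- Three named subtypes: all = 0.45 × 0.27 × 0.24 = 0.029; none = 0.55 × 0.73 × 0.76 = 0.305; mixed = 0.67.
- With the remainder as a fourth: all = 0.029 × 0.30 = 0.009; none = 0.305 × 0.70 = 0.214; mixed = 0.78.

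**5. How far this depends on the assumptions.**

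- Without stratification the mixed share is 72% (three groups) and 83% (four). With Fisher's exact test it is 55% and 65%.
- For a dose with a true rate of 30%, the stratified test gives about 32-39%, because most often no subtype is significant.
- With only two equal subtypes (25 per arm), unstratified, it is 44-46%, or 50% by Fisher.

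**6. Comparison with a direct test.** Under the same common effect, one heterogeneity (Q) test across subtypes flags a difference in about 7% of trials, and a dose-by-subtype interaction in a logistic model in about 5%.

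**7. Very small subtypes.** As an illustration, take 4 per arm. The stratified CMH test has about 3% power and is undefined in about 22% of trials. The HECSI schedule has 9 post-baseline visits, so the MMRM has 9 × 10 / 2 = 45 covariance parameters and 45 (treatment x visit) + 9 (baseline x visit) + 1 (region) + 2 (IGA) = 57 mean parameters. That is 102 parameters for 5 × 4 = 20 subjects.

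Only IGA treatment success could be computed for power. The documents give no HECSI standard deviation and no time-to-event assumption.

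**The case against.** The strongest reply is that this is headed exploratory, that 14.3.4 makes p-values nominal, and that nothing says subtypes will be compared by significance. That stands. A reader might infer that the plan intends to declare some subtypes responsive and others not, or that its main conclusions are at risk. The documents support neither reading. But exploratory status removes an error-rate claim; it does not make separate tests answer the heterogeneity question.

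The subtype mix is also unknown. The section 5.1 shares are background figures, whereas this trial enrols chronic disease with inadequate response to topical corticosteroids or where these are inadvisable (8.2). This stands too, so the sizes above are a scenario and not a forecast.

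A reader might go further, split the remainder into three subtypes of 4 per arm, and conclude that some subtype would show a dose no better than vehicle in about 70% of trials. The documents give no such split. Most of that figure is ties (strictly worse: 29%), and it falls to about 22-27% for the three named subtypes alone or with the remainder pooled. It is also not stated that all six Panel 8 categories would be used: 14.3.7.3 speaks of aetiology, and some Panel 8 categories are largely morphological.

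Finally, 14.3.12 says the analyses will be reviewed against blinded data and the statistical analysis plan finalised before the code is broken. Pooling and size rules could be added there, and so could an interaction. Nothing in the available text says they will be.

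**Conclusion.** The point holds in a limited form. The plan names a method for subtypes that cannot show whether the effect differs between them, and that small subtypes cannot support.

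Under the section 5.1 shares and the design rates of 45% and 15%, per-dose power within a subtype is roughly 24-45%, and an identical effect gives a mixed significance pattern in about 67-78% of trials. It would be too strong to say that this usually happens at any dose: at a true rate of 30% the share is about 32-39%. The figures assume one subtype per subject, the same success rates in every stratum, and the region and severity split stated above.

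The consequence is confined to how subtype results are interpreted for phase 3. The primary conclusion is unchanged. This is a cheap improvement worth making before unblinding.

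**What to change.** Amend 14.3.7.3, or the statistical analysis plan before the code is broken, as follows:

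- Define subtype by main diagnosis, so that each subject counts once.
- In the full analysis set, fit one model per endpoint with subtype and treatment-by-subtype terms. For IGA treatment success, use logistic regression with region and baseline IGA. For HECSI, use the existing MMRM extended to treatment x visit x subtype. The log-rank test has no interaction term, so time to IGA treatment success would need a regression counterpart with the same strata.
- Report subtype-specific estimates with 95% CIs and the interaction result. State that no conclusion will be drawn from separate subtype p-values.
- Set a blinded rule for pooling rare subtypes, or show them descriptively without MCP-Mod or tests.
- A dose-trend interaction on the log scale may be added as support. It should not replace the treatment-by-subtype terms, since 14.3.5 leaves the dose-response shape open among three models and the MMRM uses treatment groups.

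The cost is analysis-plan wording and modest programming, with no change to data collection, sample size or the primary analysis. The downside to state is low power: a dose-by-subtype interaction test would detect a complete lack of effect in a quarter of subjects only about 29% of the time. A non-significant result therefore does not show homogeneity.
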